## 8. OUTPUT PRESENTATIONS

Appendix 1 of the analysis plan shows conventions for presentation of data in outputs.

The templates provided with this SAP describe the presentations for this study and therefore the format and content of the summary tables, figures and listings to be provided by ██████████ Biostatistics.

Continuous variables will be summarized using descriptive statistics, i.e., non-missing observations, mean, median, standard deviation (SD), minimum, and maximum.

Categorical variables will be summarized by counts and percentages. Unless otherwise stated, the calculation of proportions will be based on the population of interest. Counts of missing observations will be included in the denominator, unless specified.

## 9. DISPOSITION AND WITHDRAWALS

All patients who provide informed consent will be accounted for in this study.

Patient disposition and withdrawals will be presented for the enrolled population. The breakdown of patients into the analysis sets (ENR, RND, FAS, SS, and PPS) will be presented.

Follow up time (days) is time between a specified event (death, end of the study or the cut-off

Document:

\\ieedc-vnasc01\\Biosdata\\Reistone\\SHR0302\\CZA55021\\Biostatistics

Author:

██████████

Version Number:

Final v1.2

Version Date:

23Mar2021

Template No: CS\_TP\_BS016 Revision 5  
Effective Date: 01Apr2018

Reference: CS\_WI\_BS005

date for dry run or SRC analysis, whichever occurred first) and the date of randomization. Follow up time will be summarized for RND.

- Follow-up time (days) = the date of event-the date of randomization +1

Number and percentage of patients allocated to treatment will be presented by previous exposure to TNF $\alpha$ /biological treatment for RND.

Number and percentage of patients allocated to treatment in each country and site will be presented by treatment group for RND.

A listing of inclusion/exclusion criteria deviations and reason for screen failure will be provided for screen failure patients.

Additionally, any protocol deviations identified during the course of the study will be listed and the number and percentage of patients in each type of protocol deviations will be summarized for the randomized population.

## **10. DEMOGRAPHIC AND OTHER BASELINE CHARACTERISTICS**

The demographic and other baseline characteristics will be presented for the FAS. The following demographic and other baseline characteristics will be reported for this study.

- Age (years)—RAVE age function
- Age groups (< 45 years/≥45 years)
- Sex
- Race
- Ethnicity
- Weight (kg)
- Height (cm)
- BMI (kg/m^2)
- Cigarette Use
- Alcohol Use
- Previous exposure to anti-TNF $\alpha$ /biological treatment
- UC disease duration
- Location and extent of patient's UC
- Baseline total Mayo score (≤10/≥10)

Descriptive statistics will be used for summarizing the patients' characteristics in each treatment group and overall. No statistical testing will be carried out for demographic or other baseline characteristics.

## 10.1 DERIVATIONS

- $BMI (kg/ m^2) = \text{weight (kg)} / \text{height (m)}^2$
- Age (years) = Year of informed consent (IC) – Year of birth, if month of IC is later than month of birth, or if month of IC is equal to month of birth but day of informed consent is later than or equal to day of birth;

Age (years) = Year of informed consent – Year of birth – 1, otherwise.

In this case, if one patient is more than 45 years old but less than 46 years old, then this patient will be presented as age 45.

- UC disease duration (years) = (Date of informed consent – Date of Diagnosis +1)/365.25, presented to 1 decimal place.

For partially missing dates, the UC disease duration (years) will be based on imputed values. If the date part is missing while year and month present, 15th of the month will be used for imputation. If both date and month part are missing while year presents, July 1st will be used for imputation.

## 11. MEDICAL HISTORY

Medical History will be coded using Medical Dictionary for Regulatory Activities (MedDRA) Version 21.1 or higher version. Data captured on the Medical History page of the CRF will be presented by body system description (SOC) and Preferred Term (PT) for FAS.

Number and percentage of patients with at least one medical history or one complication of UC will be presented by treatment group for FAS.

Detailed information of medical history including medical history term, year diagnosed, ongoing or not, and whether this conditions or events is a complication of Ulcerative Colitis will be listed for FAS.

## 12. MEDICATIONS AND PROCEDURES

Prior medications are those medications that were stopped prior to first study treatment. Concomitant medications are medications taken at least once after first study treatment. Medications stopped on the same day as first study treatment will be considered as prior medication only.

Prior and concomitant medications will be coded using the World Health Organization Drug Dictionary (WHO Drug Global 01Sep2018\_B3). The PT and Anatomical Therapeutic Chemical (ATC) Classification System level 2 will be used for tabulation. The summary tables will show the number and percentage of patients by PT and ATC level 2, for each treatment group and overall. Only concomitant medications will be summarized. The descriptive summaries for concomitant medications will be presented for the SS. Missing or partial dates for medications will be handled according to Appendix 2 of this analysis plan. In the case where it is not possible to define a medication as prior or concomitant, the medication will be classified by the worst case; i.e. concomitant. For the summaries of concomitant medications, patients who take the same medication (in terms of the PT), more than once will only be counted once for that medication. Prior medications will be listed only.

The detailed information of prior and concomitant medication use including medication name, start date, end date, ongoing or not, primary reason for use, total daily dose, frequency and route of administration, etc. will be listed. Prior and concomitant medications will be listed separately.

The detailed information of procedures will be collected on the “Procedures” form of Electronic Case Report Form (eCRF) including procedure name, start date, end date, ongoing or not, and primary reason for use. Procedure name will be coded using Medical Dictionary for Regulatory Activities Version 21.1 or higher version. Procedures information be will be listed.

## 13. STUDY MEDICATION EXPOSURE

Exposure to study medication will be presented for SS by treatment group.

The date of first study medication administration will be taken from eCRF “Noncompliance with study treatment ” form if available (Site will check medical chart and make the first dose record on this eCRF form). In case of not available, the first dose date from the diary data will be used. The date of last study medication will be taken from the eCRF “End of Treatment”

Document: \\ieedc-vnasc01\Biosdata\Reistone\SHR0302\CZA55021\Biostatistics  
Author: [REDACTED]

Version Number:  
Version Date:

Final v1.2  
23Mar2021

Template No: CS\_TP\_BS016 Revision 5  
Effective Date: 01Apr2018

Reference: CS\_WI\_BS005

form. In the case of missing data on the eCRF, the last dose date from diary data will be used

The study medication intake for each day will be taken from the diary “Time of Dosing” and “# Tablets Taken” items. The following information will be summarized for each treatment group in treatment phase, extension phase and overall:

- Duration of Exposure (days)
- Planned number of study drug tablets
- Actual number of study drug tablets
- Number of Dosing Days
- Cumulative Dose (mg)
- Average Daily Dose (mg/day)

### 13.1 DERIVATIONS

- Duration of exposure(days)= Last date of exposure in corresponding phase– First dose date in corresponding phase +1

When the start or stop date is missing, then the exposure will be treated as missing. Interruptions, compliance, and dose changes are not taken into account for duration of exposure.

- Planned number of tablets

The investigational product taken during the 16-week treatment period will be double blind. In order to preserve blinding and ensure patients compliance, all arms are administered under twice daily dosing regime and placebo is used according to the schedule in table 1. At each dosing time (morning, am or afternoon, pm), patient will be taking two tablets. The treatments are given twice daily and it is assumed that the patient should take medication from the morning of the visit day at which their medication is initially dispensed to the afternoon of their last visit date. At each dosing time (morning, am or afternoon, pm), patient will be taking two tablets. In one day, a patient will take a total of four tablets, two tablets in the morning and two tablets in the afternoon. For example, if the initial dispense date is Day 1 and the last visit date is Day 10, then the patient should have taken 2 tablets at am on Days 1 to 10; hence, the total number of planned tablets at am would be  $10 \times 2 = 20$ .

- Actual number of tablets=Sum of tablets captured on Patient Diary
- Number of dosing days= Last date of exposure in corresponding phase – First dose date in corresponding phase +1(-off drug period)

Number of dosing days is the number of days with non-zero tablets.

- Cumulative dose (mg)= Sum of SHR0302 dose based on Patient Diary.

In one day, a patient will take a total of four tablets, two tablets in the morning and two tablets in the afternoon. According to treatment arm and the time of dosing, the average dose of SHR0302 per tablet are calculated and listed in below table (Table 1).

According to the actual treatment group of a patient, SHR0302 dose per day will be calculated by the following formula:

SHR0302 dose per day=number of tablets taken at am\* average SHR0302 dose per tablet (am) +number of tablets taken at pm\* average SHR0302 dose per tablet (pm)

Cumulative dose will be sum of SHR0302 dose per day based on Patient Diary.

Table 1: Study drug packaging design and average dose per tablet

Study Arms-all BID	Dose 1(am)	Average dose per tablet (am)	Dose 2 (pm)	Average dose per tablet(pm)
4mg QD	4mg+placebo	SHR0302 2mg per tablet	Placebo+placebo	SHR0302 0mg per tablet
8mg QD	4mg+4mg	SHR0302 4mg per tablet	Placebo+placebo	SHR0302 0mg per tablet
4mg BD	4mg+placebo	SHR0302 2mg per tablet	4mg+placebo	SHR0302 2mg per tablet
Placebo	Placebo+placebo	SHR0302 0mg per tablet	Placebo+placebo	SHR0302 0mg per tablet

- Average daily dose(mg/day) = Cumulative dose (mg)/ Number of dosing days (days)

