6. Vital signs include resting blood pressure, heart rate, and body temperature. It is advised to measure them before any procedures or questionnaires.
7. Adverse events and Serious Adverse Events to be collected from the start of the study drug (visit 2) until the Follow-Up contact. However, any serious adverse events will be recorded from the time of consent.
8. Investigator has the option to use PPD test, QuantiFERON Gold test or T-Spot for TB screening. Subjects who have previously receive BCG vaccination will be tested by QuantiFERON Gold test/or T-Spot test, and the result will determine the subject eligibility for participation.
9. Urine pregnancy test to be done in females of childbearing potential only

10. β -Human Chorionic Gonadotrophin(β -HCG) to be done in females of childbearing potential at screening visit, and only to be done if urine pregnancy test positive at other study visits.
11. Early withdrawal visit should be done within 2 weeks after last dose/decision of withdrawal.
12. Only to be conducted in the early withdrawn subjects.

15. FSH to confirm postmenopausal status at screening visit only.

6. Study Treatments

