## 14.1 DERIVATIONS

- Compliance (%) = (Amount Dispensed - Amount Returned - Amount Lost) \* 100 / (Planned number of tablets to be taken)

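### SAP 13.1 counts planned tablets up to the last visit, so adherent patients who withdraw early can score below 80% compliance; average daily dose also ignores wholly missed days

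*SAP*

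**What the plan says.** **Planned tablets.** SAP 13.1 assumes that medication is taken "from the morning of the visit day at which their medication is initially dispensed to the afternoon of their last visit date". The daily count is fixed: "In one day, a patient will take a total of four tablets, two tablets in the morning and two tablets in the afternoon". The worked example has the same end point: "if the initial dispense date is Day 1 and the last visit date is Day 10", the plan is 20 morning tablets.

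**Compliance.** SAP 14.1 divides tablets dispensed, less those returned or lost, by "Planned number of tablets to be taken". SAP 14 sets the non-compliance cut at 80%. It gives no definition of planned tablets, so 13.1 supplies the only one. SAP 7.3 uses compliance before Week 8, split at 80%, as an exploratory subgroup for the primary endpoint.

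**Last dose.** SAP 13 already obtains this date: "The date of last study medication will be taken from the eCRF" End of Treatment form, with the diary as fallback. It serves duration of exposure but not planned tablets.

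**Withdrawal visit.** Protocol 5.12, footnote 11: "Early withdrawal visit should be done within 2 weeks after last dose/decision of withdrawal". Footnote 12 and Protocol 6.1 place drug accountability for withdrawn patients at that visit.

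**Average daily dose.** SAP 13.1 divides cumulative mg by dosing days and adds: "Number of dosing days is the number of days with non-zero tablets". It also gives a formula that subtracts an off-drug period, which it does not define. Both versions remove days without drug.

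**The concern.** Compliance should say how much of the drug that was due a patient took. For a withdrawn patient, this denominator also counts days after drug had ended, so the score depends partly on how soon the visit took place. That sits badly with SAP 14 and Protocol 6.5, which both measure non-compliance against the dosing instructions.

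The error carries into the subgroup analysis. A patient who withdraws before Week 8 has no Week 8 score and is a failure under the NCF rule in SAP 15.1.1. Moving adherent withdrawals into the below-80% subgroup adds failures by rule to that subgroup. A reader could take the result as poor adherence causing non-response.

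Average daily dose matters because SAP 3.1 says the study is meant to select one or two doses. This row is the natural place to see whether the arms received their intended doses, and it cannot register a day on which nothing was taken.

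**Working it through.** **1. The plan's own example.** Dispensed Day 1, last visit Day 10: (10 − 1 + 1) × 2 = 20 morning tablets, as stated. The rule is inclusive of both dates.

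**2. Compliance of a fully adherent withdrawn patient.** Let D be the days on drug with every tablet taken, and g the days from last dose to the withdrawal visit. Compliance = 4D / [4(D + g)] = D / (D + g).

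For D = 28 and g = 14: 28 × 4 = 112 taken, 42 × 4 = 168 planned, 112/168 = 66.7%.

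| Days on drug | 3-day gap | 7-day gap | 14-day gap |
|---|---|---|---|
| 14 | 82.4% | 66.7% | 50.0% |
| 28 | 90.3% | 80.0% | 66.7% |
| 42 | 93.3% | 85.7% | 75.0% |
| 55 | 94.8% | 88.7% | 79.7% |

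D / (D + g) is below 0.80 exactly when D < 4g. The largest D that fails is therefore 55 for a 14-day gap, 27 for 7 days and 11 for 3 days. Ending the count at the last dose gives D/D = 100% in every cell.

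**3. The subgroup.** SAP 14 restricts this version to tablets before Week 8. If that means Day 0 to Day 55 (56 days), planned days cannot exceed 56. With a 14-day gap, 44 days on drug gives 44/56 = 78.6% and 45 days gives 45/56 = 80.4%, so the subgroup limit is 44 days rather than 55. The 7-day and 3-day limits do not change, because 27 + 7 and 11 + 3 are both below 56.

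**4. Completers, for comparison.** With Week 8 (Day 56) as the last visit, planned tablets are 57 × 4 = 228. A patient who takes everything through the Day 56 morning dose scores 226/228 = 99.1%; one who takes an exact 56-day supply scores 224/228 = 98.2%. Neither is misclassified.

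**5. Average daily dose.** Tablets taken on 28 of 56 days, 8 mg on each:
- Cumulative dose: 28 × 8 = 224 mg.
- SAP rule: 224/28 = 8.0 mg/day.
- Over all 56 days: 224/56 = 4.0 mg/day, the nominal dose of the 4 mg QD arm.
- Over duration of exposure, if dosing is on alternate days and the last dose falls one day before the end of the 56 days: 224/55 = 4.07 mg/day.

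A one-week interruption in 56 days gives (49 × 8)/49 = 8.0 under the SAP and 392/56 = 7.0 over all days.

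**6. What the row does show.** In the 4 mg BD arm with every afternoon dose missed, 56 × 4 = 224 mg and 224/56 = 4.0 mg/day. Missed active tablets within a day do lower the average.

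**The case against.** **Fourteen days is the maximum gap.** Protocol 5.8 asks sites to bring the patient back as soon as possible. With a 3-day gap only patients on drug for 11 days or fewer are affected. The planned dropout is 8% of 152, or 0.08 × 152 ≈ 12 patients over four arms. This stands and limits the size, but the rule is still wrong for the patients it reaches.

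**Skipped days are visible elsewhere.** The alternate-day patient in step 5 would show 28 dosing days, 224 mg cumulative dose and compliance of 112/228 = 49%. Dose per day on drug is also a recognisable quantity. Both points stand. The fault is confined to one row, and relabelling that row would be an acceptable remedy.

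**Completers.** A reader might infer that adherent completers are mislabelled too, taking the 2-week follow-up as the last visit: 226/284 = 79.6% for a patient who declines the extension (Day 0 to Day 70, 71 × 4 = 284). The documents do not support this. The sentence in SAP 13.1 sits in a paragraph on the 16-week treatment period, and drug accountability at follow-up applies only to withdrawn patients. The figure is also fragile: counting the Day 56 afternoon dose gives 228/284 = 80.3%.

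**Comparison across arms.** A reader might also infer that average daily dose is not comparable between QD and BD arms, because an afternoon-only day counts 0 mg in one and 4 mg in the other. By SAP Table 1 those are the amounts received, so this is not a defect.

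**Ending at last dose for everyone would hide non-compliance.** A patient who stops unprompted after 28 days but attends Week 8 would score 112/112 = 100%, against 112/228 = 49% now. This objection is correct, and the fix below is restricted because of it.

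**Conclusion.** The point holds for early-withdrawn patients and for one row of the exposure table. A fully adherent patient who withdraws is labelled non-compliant whenever days on drug are fewer than four times the gap to the visit: up to 55 days at the 14-day limit, 27 at 7 days and 11 at 3 days. Average daily dose returns the nominal dose however many whole days are skipped.

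This assumes that the withdrawal visit is the last visit for a withdrawn patient and that the planned count in SAP 14 is the one in SAP 13.1. The documents give no distribution of gaps, so the number affected is unknown. At the planned dropout it would be at most about 12. Whether withdrawal differs by dose is also unknown.

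The primary FAS analysis is unaffected. The documents do not say that compliance below 80% removes a patient from the per-protocol set, so no effect there can be claimed. The change is worth making because the affected tables and subgroup would otherwise mislead, and the last dose date it needs is already collected.

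**What to change.** **(a) Planned tablets, SAP 13.1 and 14.1.** For early-withdrawn patients only, end the count at the last dose date on the End of Treatment form, with the diary as fallback as in SAP 13. For all others, end it at the last on-treatment visit of the phase (Week 8 or Week 16), never at follow-up. Unprompted stopping while still attending visits then remains non-compliance. Add a cross-reference from SAP 14 to this definition. State whether it covers withdrawal during the extension, since Protocol 5.8 defines early withdrawal only up to Visit 5.

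**(b) Dose intensity, SAP 13.1.** Divide cumulative dose by duration of exposure, or label the present row as dose per dosing day. In either case add cumulative mg as a percentage of planned mg by arm, using the planned period in (a) and SAP Table 1. This last row is needed because duration of exposure cannot detect early stopping: an 8 mg QD patient who quits after 28 days still shows 224/28 = 8.0 mg/day, whereas 224/(57 × 8) = 224/456 = 49% of planned mg.

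**Cost.** SAP wording, two re-programmed derivations and one added row, from data already collected. Average daily dose will look slightly lower. A withdrawn patient who stopped taking tablets before the decision to withdraw is scored only to the last dose, so that lapse is not counted. The exposure and compliance sections name no source for a decision date, which is why the last dose date is preferred.

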## 14. STUDY MEDICATION COMPLIANCE

Compliance to investigational product will be presented for the SS. Compliance with investigational product is derived from data recorded on the eCRF “Drug Accountability” and “Noncompliance With Study Treatment” pages. Compliance will be calculated as the number of tablets taken (amount dispensed-amount returned-amount lost) divided by the planned number of tablets to be taken. The compliance rate will be categorized as <80 , ≥80 to ≤100 and >100. Compliance in treatment phase and extension phase will be summarized and

Document: \\ieedc-vnasc01\Biosdata\Reistone\SHR0302\CZA55021\Biostatistics  
Author: [REDACTED]

Version Number:  
Version Date:

Final v1.2  
23Mar2021

Template No: CS\_TP\_BS016 Revision 5  
Effective Date: 01Apr2018

Reference: CS\_WI\_BS005

presented. Furthermore, Compliance will be calculated for kits dispensed at baseline, Week 4, Week 8, Week 12, other visits, unscheduled visit and overall. Overall Compliance before Week 8 used in subgroup analysis in section 7.3 is defined as taking more than or equal to 80% of study drug products before Week 8. Overall Compliance before Week 8 will be calculated as the total number of tablets taken before Week 8 divided by the planned number of tablets to be taken before Week 8.

In addition, the following information will be summarized:

- Overall non-compliance

Overall non-compliance is defined as taking less than 80% of study drug products as directed by the dosing instructions.

- Reason for non-compliance with study treatment

A by-patient listing will include any reasons for noncompliance with study treatment.

## 14.1 DERIVATIONS

- Compliance (%) = (Amount Dispensed - Amount Returned - Amount Lost) \* 100 / (Planned number of tablets to be taken)

## 15. EFFICACY ENDPOINTS

### 15.1 PRIMARY ENDPOINT

Mayo score is an instrument designed to measure disease activity of ulcerative colitis. Mayo score ranges from 0 to 12 points. It consists of 4 subscores, each graded from 0 to 3 with higher scores indicating more severe disease. The four subscores are listed below.

- Stool frequency (0-3)
- Rectal bleeding (0-3)
- Findings of colonoscopy (0-3)
- Physician global assessment (0-3)

The Physician global assessment (PGA) is a clinician-reported assessment that reflects "the patient's recorded symptoms, the proctoscopic appearance of the rectosigmoid mucosa, and

Document: \\ieedc-vnasc01\Biosdata\Reistone\SHR0302\CZA55021\Biostatistics

Author: [REDACTED]

Version Number:

Final v1.2

Version Date:

23Mar2021

Template No: CS\_TP\_BS016 Revision 5  
Effective Date: 01Apr2018

Reference: CS\_WI\_BS005

other pertinent clinical indexes, such as physical findings and the patient's performance status.

9-point modified Mayo score is the Mayo score excluding PGA subscore, hence the maximum is 9 points and minimum 0 point. By removing the PGA, it removes the subjective view/assessment from the physicians hence reducing bias. It is also a recommended assessment by the regulators. 9-point modified Mayo score will be collected as a primary endpoint at week 8.

The primary endpoint is the percentage of patient achieving clinical response at week 8 which is defined as decrease from baseline in 9-point modified Mayo score of at least 2 points and at least 30%, with an accompanying decrease in the subscore for rectal bleeding of at least 1 point or absolute subscore for rectal bleeding of 0 or 1.

